## Analysis Plan:

Primary and Secondary Outcome Measures: The Profile of Hearing Aid Performance (PHAP, Cox & Gilmore, 1990) and the Hearing Handicap Inventory for the Elderly (HHIE, Ventry & Weinstein, 1982) served as the instruments for the primary and secondary outcome measures, respectively. These instruments were administered in the first in-person session before participants were fitted with hearing aids (S1) to establish baseline, approximately six weeks later (S2), and for a final time approximately six months after the initial fitting (S2). Benefit, computed as the difference in scores on these instruments, S1 score – S2 score and S1 score – S3 score, were the outcome measures of interest. The benefit measures are labeled HHIE-total benefit. The benefit for the PHAP is termed Profile of Hearing Aid Benefit (PHAB) which can be calculated as a global score (PHAB global) for five of the seven subscales pertaining to speech communication. These five subscales are: Familiar Talkers (FT) Ease of Communication (EC), Reverberation (RV), Reduced Cues (RC), and Background Noise (BN). Finally, these scores can be computed from the entire instrument (66 items) or from an abbreviated version, the Abbreviated Profile of Hearing Aid Benefit (APHAB), a 24item subset.

Sample Size and Statistical Power: To determine the sample size needed, estimates of treatment effects, effect sizes, and common standard deviations for the primary and secondary outcome measures were derived from [name] et al. (2017). As in the present randomized controlled trial (RCT), [name] et al. (2017) obtained unaided or pre-fit measures for the PHAP and the HHIE total initially, with aided PHAP and HHIE total scores obtained at the conclusion of a 6-week trial. For the primary outcome measure, the PHAB-global, the mean treatment effect for AB service delivery relative to placebo control was 11 in [name] et al. (2017). Incidentally, the common standard deviation was also 11, yielding a Cohen's d effect size of 1.0 for the PHAB-global. As a non-inferiority RCT, a margin must also be specified a priori, which effectively represents a

2

boundary between clinically significant inferior and non-inferior outcomes. The most widely adopted convention is to set the margin to ½ the effect of the standard of care (Audiology based – AB) relative to placebo, or ½ the pooled standard deviation (D'Agostino et al., 2003; Norman et al., 2003). Following the latter convention, a non-inferiority margin of 5.5 was established for the PHAB global. It also translated, in the pertinent region of the PHAP rating scale, to a change of about ½ scale unit on the 7-point PHAP response scale, which would likely be considered a minimally clinically important change from unaided to aided performance. For the secondary outcome measure, HHIE-total benefit, the treatment effect for AB service delivery relative to placebo was 13 with a common standard deviation of 13 as well ([name] et al., 2017), consistent with observations in several prior studies using the HHIE (Chisolm et al., 2007). Accordingly, following the same rationale described for the PHAB-global, the non-inferiority margin for the HHIE-total benefit score was set to 6.5.

nQuery Advisor (V8.3.1) was used to estimate the sample size needed for the non-inferiority analyses of the comparative effectiveness of fitting methods. Two separate one-sided significance tests of group differences, AB vs Consumer Decides (CD) and AB vs Easy Fitting (EF), were planned for the outcome measures. As a result, the significance level was set to 0.025 (0.05/2). Power calculations estimated that when the sample size in each group was 64, a two group one-sided 0.025 significance level t-test for multiple (two) comparisons will have 80% power to reject the null hypothesis that the test (CD or EF) and standard (AB) are not non-inferior [the difference in means,  $\mu$ CD- $\mu$ AB or  $\mu$ EF- $\mu$ AB, is 5.5 (PHAB), or is 6.5 (HHIE benefit), or farther from zero in the same direction] in favor of the alternative hypothesis. The alternative hypothesis is that the means of the two groups are non-inferior, assuming the expected difference in means is 0 and the common standard deviation is 11 and 13 for the PHAB global and HHIE total benefit measures, respectively. Thus, with three groups and a required N of 64 per group, a total of 192 participants were needed.

3

Based on prior work of a similar nature ([name] et al., 2019; [name] et al., 2017), it was assumed that about 36% of those who enrolled would have audiometrically defined normal hearing (better-ear PTA4 < 20 dB HL), better than the sponsor-required range of mild to moderate audiometric hearing loss. As a result, a total of 389 individuals (130 per group) were targeted for study completion (Session 3) so that at least 249 individuals (83 per group) with mild or moderate hearing loss would be included in the analyses. Assuming, again based on experience with similar RCTs, that overall attrition from study enrollment to the 6-month follow-up would be about 35%, the target enrollment at Session 1 was established to be 591 (197 per group).

A total of 584 adults enrolled at Session 1, but both the percentage with normal hearing and the attrition rates were lower than anticipated. In the end, enrollment of 584 participants in Session 1 resulted in 172, 171 and 180 adults with mild or moderate audiometric hearing loss assigned to the AB, CD, and EF groups. Of these, 152, 133, and 138 completed all three sessions for groups AB, CD, and EF, respectively. Based on the desired sample size of 64 per group for the primary (PHAB global) and secondary (HHIE total benefit) outcome measures, as well as the sample size of 83 per group targeted for eventual APHAB global analyses, the intention-to-treat (ITT) and per-protocol (PP) analyses were sufficiently powered. In addition, when the numbers of those with mild or moderate audiometric hearing loss in each group were tabulated, ITT analyses were sufficiently powered (group sizes > 64) to perform sensitivity analyses for each hearing-loss severity separately using the primary and secondary outcome measures.

As noted, in addition to the PHAB-global and HHIE-total benefit primary and secondary outcome measures, a measure of quality of life, the PROMIS-10 Global (Hays et al., 2009), was obtained at Sessions 1 and 3. In particular, the raw PROMIS physical-health and mental-health scores were computed following PROMIS-10 guidelines, and these two subscale scores represented an additional long-term outcome measure obtained in this RCT. No non-inferiority

4

margin was established *apriori* for this measure because it was not the primary or secondary outcome and because few data were available from RCTs of hearing-aid interventions that had used the PROMIS-10 Global.

**Analyses:** Some participants in each branch decided to withdraw from the study prior to completion. All participants remained in the branch to which they were randomly assigned at study outset. SAS Version 9.4 was used to impute missing data using the Markov Chain Monte Carlo (MCMC) method (n=20 imputations) and the multivariate-normal approach. Both ITT and PP analyses were performed, as has been recommended (Rehal et al., 2016). After addressing the missing data, initial analysis of the effects of fitting method followed the recommendations by the International Conference on Harmonization (2001; 1998) and CONSORT (Piaggio et al., 2001; Piaggio et al., 2006). The primary focus of the analyses is the comparative effectiveness of each self-fitting method (CD, EF) to best practices (AB). Finally, sensitivity analyses were performed by examining the outcomes separately for those with mild versus moderate audiometric hearing loss. All statistical analyses used SPSS Version 29.0.1.0. This included boot-strapped (n=1000; Biascorrected and accelerated, BCa) General Linear Model analyses, t-tests, means, and 95% confidence intervals.

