13.4.5 Randomizing Participants [AudU]

- **This step can only be completed by the Unblinded Audiologist (AudU).**
- Connect to NU VPN using the “GlobalProtect” icon on the iPad homescreen if you are not at NU.
- Select the “REDCap Login” icon on the iPad homescreen.
- Log into REDCap using your NetID and password.
- Click on **“Add/Edit Records”**
- “Choose an existing Record ID” using the drop-down menu
- The directions for randomization are displayed on the original REDCap screen on the other browser tab where the data entry process has halted.
- Select “1-Randomization”
- Click the circular button in the branch assignment column for the record ID for your participant.
- This will take you to a form where you will confirm “Test Site” in the “Group Randomization” division halfway down on the screen.
- Click on the “Randomize” button.
- Confirm “Test Site” and “Degree of Hearing Loss” on the pop-up window.
- Click on the “Randomize” button.
- A pop-up screen will display the group assignment.
- Click on the “Close” button to close pop up window.
- Change the “Complete?” drop down field to “Complete.”
- Click the “Save and Exit Form” button.
- **Close this tab** by clicking on the small “x” in the tab label.
- Return to the other open tab and **reload the page** by clicking on the “reload” button in the address bar.

[Continue to Post Randomization](#)

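### The only tests tied to the non-inferiority margins are unadjusted t-tests on benefit, and the General Linear Model listed beside them has no stated terms

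*SAP*

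**What the plan says.** The SAP (Primary and Secondary Outcome Measures) defines the outcome as a change score: "Benefit, computed as the difference in scores on these instruments", that is S1 minus S2 and S1 minus S3. Under Sample Size and Statistical Power, "Two separate one-sided significance tests of group differences, AB vs Consumer Decides (CD) and AB vs Easy Fitting (EF), were planned", and the margins of 5.5 (PHAB global) and 6.5 (HHIE total benefit) enter through "a two group one-sided 0.025 significance level t-test for multiple (two) comparisons".

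The Analyses paragraph lists bootstrapped "General Linear Model analyses, t-tests, means, and 95% confidence intervals". It gives the General Linear Model no factors or covariates and does not say whether the model or the t-test supplies the interval that is read against the margin.

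Severity is used only to divide the sample: the SAP states that "ITT analyses were sufficiently powered (group sizes > 64) to perform sensitivity analyses for each hearing-loss severity separately". Site does not appear in the SAP's analysis text.

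Protocol sections 3.0 and 11.0 describe random assignment by degree of hearing loss within site. At randomisation the audiologist must "Confirm “Test Site” and “Degree of Hearing Loss” on the pop-up window" (section 13.4.5). Section 3.0 also refers to a full protocol in an appendix, which is not among the supplied documents.

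**The concern.** The randomisation used site and hearing-loss category, and S1 scores exist for both instruments, so the usual adjustment variables are already in the database. The one analysis linked to the margin uses none of them as a term. Subtracting S1 fixes its coefficient at 1; entering it as a covariate lets the data estimate that coefficient, which gives a narrower interval unless 1 happens to be the right value.

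Two things are at stake. The first is interval width, which matters most if a self-fit arm is truly somewhat worse than AB but within the margin, and in the smaller severity groups. The second is the decision rule. A reader cannot tell whether a t-test, an unadjusted model or an adjusted model decides non-inferiority. The SAP is written in the past tense with final counts, so a choice made now could be made with the results known.

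**Working it through.** **Inputs from the SAP.** SD 11 (PHAB) and 13 (HHIE); margins 5.5 and 6.5; one-sided 0.025; planned true difference 0; 64 per group. Assigned with mild or moderate loss: AB 172, CD 171, EF 180. Completers among them: AB 152, CD 133, EF 138.

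**Assumptions not in the documents.** Correlation r between S1 and follow-up, 0.3 to 0.7; ratio k of follow-up SD to S1 SD, taken as 1 and then varied; true deficit of the self-fit arm, 0 to 3 points.

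**Step 1: the plan's own figure.** The noncentrality is 5.5 / (11 × √(2/64)) = 5.5 / 1.9445 = 2.83 on 126 degrees of freedom, which gives power of 80.15%. HHIE is identical because 6.5/13 = 5.5/11 = 0.5. The stated 64 per group therefore reproduces as an unadjusted two-sample t-test.

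**Step 2: what S1 adjustment does.** With s the S1 standard deviation:
- variance of benefit = s²(1 + k² − 2rk)
- variance after adjusting for S1 = s²k²(1 − r²)
- difference = s²(1 − rk)², never negative, and zero only when rk = 1

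At k = 1 the SD is multiplied by √((1 + r)/2), which is 0.806, 0.866 and 0.922 for r = 0.3, 0.5 and 0.7. The interval narrows by 19%, 13% and 8%.

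**Step 3: full set, AB 152 versus CD 133.** The unadjusted standard error is 11 × √(1/152 + 1/133) = 1.306. Power is from the noncentral t with noncentrality (5.5 − deficit) / standard error; the adjusted columns multiply the standard error by the factor in step 2.

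| True deficit | Unadjusted | Adjusted, r = 0.7 | Adjusted, r = 0.3 |
|---|---|---|---|
| 0 | 98.7% | 99.5% | 99.9% |
| 1 | 93.0% | 96.1% | 98.9% |
| 2 | 76.1% | 82.6% | 91.2% |
| 3 | 47.9% | 54.3% | 65.8% |

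Simulation with S1 as a covariate (4,000 runs, r = 0.5, deficit 2) gave 77% unadjusted and 88% adjusted, in line with the formula (76% and 87%).

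**Step 4: severity groups, true difference 0.** The SAP gives only a floor, group sizes above 64. The 172 + 171 + 180 = 523 assigned, spread over six arm-by-severity cells, average about 87.

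| Per arm | Unadjusted | Adjusted, r = 0.7 | Adjusted, r = 0.3 |
|---|---|---|---|
| 65 (floor) | 80.8% | 86.6% | 93.9% |
| 87 (average) | 90.7% | 94.5% | 98.3% |

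At 65 per arm the PHAB half-width falls from 3.82 to between 3.52 and 3.08, and the HHIE half-width from 4.51 to between 4.16 and 3.64. These are ITT groups. The figures count imputed participants as observed, so they are upper values.

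**Step 5: sensitivity to the variance ratio.** At 65 per arm with r = 0.7, adjusted power is 94.6% for k = 0.8, 82.1% for k = 1.2 and 80.8% for k = 1.4. The last is no gain, as expected near k = 1/0.7 = 1.43.

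The gain from site and stratum cannot be computed from the documents.

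**The case against.** The strongest reply is that little turns on this under the plan's own assumptions. With a true difference of 0 the completers already give 98.7% power, and the gain at 1 to 3 points depends on deficits, a correlation and a variance ratio that the documents do not give. That stands, and it is why ranges are shown. It is also fair that 65 per arm is only the floor for the severity groups, that those are sensitivity analyses, and that one-sided 0.025 matches a 95% interval, so what is unstated is the model behind the interval and not its level.

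Two other replies are weaker. That S1 is already in the outcome does not meet the point, because subtraction is not covariate adjustment. That severity is analysed separately does not adjust the main comparison. One might also note that the S1 PHAP is completed after randomisation (Protocol section 13.4.6). It precedes fitting, however, and the same score already enters the benefit measure.

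A reader might infer that the unadjusted comparison is biased, that the trial is underpowered, or that the analysis was in fact run without covariates. The documents support none of these. Randomisation makes the unadjusted contrast unbiased. The stated sample size is right for the stated test, and enrolment exceeded it. The model's terms are simply not given, and the full protocol cited in section 3.0 may give them.

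**Conclusion.** The point holds as a matter of precision and of an unstated decision rule. The supplied SAP ties the margins only to an unadjusted t-test, lists a General Linear Model without terms, and names no adjustment for S1 score, site or hearing-loss stratum. Adjusting for S1 would narrow the intervals by 8% to 19% if variances are equal and r lies between 0.3 and 0.7, and by nothing as r times the SD ratio approaches 1. The effect on full-set power is negligible at a true difference of 0. It is material only if a self-fit arm is truly worse by a point or more, or in the smaller severity groups. If the adjusted model is reported as post hoc, the t-test still decides and none of this gain reaches the decision; the adjusted model then only sharpens the supporting estimate.

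**What to change.** For each of S2 and S3, and for PHAB global and HHIE total benefit, specify: benefit = arm + S1 score + site + hearing-loss stratum as randomised. Keeping benefit as the outcome leaves the sign and the margins unchanged. Report the CD−AB and EF−AB 95% intervals against 5.5 and 6.5, in the full set and within the severity groups, keeping the stratum term there only where it still varies.

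State which model's interval decides non-inferiority. Make the adjusted model primary only if prespecification can be shown. Otherwise keep the t-test as the deciding analysis and report the adjusted model beside it, labelled post hoc. If the full protocol already gives the model terms, repeat them in the SAP.

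The cost is SAP wording and a set of extra model runs on data already collected: two outcomes, two time points, ITT and per-protocol, full set and severity groups, over the 20 imputations where they apply. Margins, sample size and the planned test do not change.

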2.0 Overview

Hearing aids are the most common and appropriate treatment for most adults with hearing loss. Approximately 40% of those over the age of 60 years are affected by hearing loss. Only 20% of these individuals purchase and use hearing aids. The Over-the-Counter Hearing Aid Act of 2017 is designed to decrease cost and make it easier for consumers to purchase and use hearing aids. The best methods for distributing hearing aids without the involvement of a professional are not known.

The overall goal of this proposal is to compare two over-the-counter (OTC) models of hearing aid distribution and fitting against audiology-based best practice (AB). This goal will be achieved through the following specific aim:

To determine whether brief consumer decides (CD) and Efficient Fit (EF) models for hearing aid provision are non-inferior to current audiology-based best practices (AB).

Outcomes of hearing aid use when the hearing aid is fit using one of three possible methods (AB, CD, and EF) will be measured after 6 weeks and 6 months of hearing aid use. The basic questions being asked are whether outcomes are similar for the three methods of fitting hearing aids.

The results of the study would help inform professionals, policy makers, as well as patients about whether alternate methods of distributing and fitting hearing aids can lead to outcomes similar to those achieved with a licensed healthcare provider.

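### The SAP's non-inferiority null contradicts itself: it is labelled not non-inferior, but for test minus AB the region printed is the one where self-fitting is better

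*SAP*

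**What the plan says.** The SAP (Primary and Secondary Outcome Measures) defines benefit as the Session 1 score minus the Session 2 or Session 3 score. Under Sample Size and Statistical Power it gives AB an effect over placebo of 11 on PHAB-global, and for HHIE-total benefit it says that "the treatment effect for AB service delivery relative to placebo was 13".

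The same section calls the margin a "boundary between clinically significant inferior and non-inferior outcomes" and sets it at 5.5 for PHAB-global and 6.5 for HHIE-total benefit, both without a sign. It announces one-sided tests at 0.025, in which "AB vs Consumer Decides (CD) and AB vs Easy Fitting (EF), were planned for the outcome measures". The power statement is the chance to "reject the null hypothesis that the test (CD or EF) and standard (AB) are not non-inferior". A bracket then explains that null: the difference in means, written as CD minus AB or EF minus AB, "is 5.5 (PHAB), or is 6.5 (HHIE benefit), or farther from zero in the same direction". The alternative is given in words only: "The alternative hypothesis is that the means of the two groups are non-inferior".

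The Analyses paragraph lists bootstrapped General Linear Model analyses, "t-tests, means, and 95% confidence intervals". It gives no signed hypothesis and no criterion for a confidence limit. Protocol section 2.0 (Overview) states the single specific aim, which is to find out whether CD and EF "are non-inferior to current audiology-based best practices (AB").

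**The concern.** On both benefit scales a larger value is better. A test-minus-AB difference of 5.5 or 6.5, or farther from zero in that direction, therefore means that the self-fit arm outperforms AB by the margin or more. The SAP attaches this region to the null it calls not non-inferior. The label and the region cannot both be right for the subtraction printed.

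This matters because the bracket is the only place in either document where the non-inferiority hypothesis appears with numbers and an order of subtraction. Anyone checking the reported conclusion against the plan has to set aside its literal wording to get the right test.

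**Working it through.** **Direction of the scales.**
- Benefit = S1 - S2 or S1 - S3 (SAP, Primary and Secondary Outcome Measures).
- AB minus placebo is +11 on PHAB and +13 on HHIE benefit (SAP, Sample Size and Statistical Power).
- On the raw HHIE a higher score means more difficulty, because protocol 13.4.1 disqualifies scores of 4 or less. A positive S1 - S2 is therefore an improvement.
- The documents do not describe PHAP item scoring. The PHAB direction rests on the first two facts.

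**Two readings of the null.** Let d = test minus AB and m = the margin.
- Literal: H0 is d ≥ +m, rejected when (observed d - m)/SE < -t.
- Intended: H0 is d ≤ -m, rejected when (observed d + m)/SE > t.

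**The plan's own figure first.** Inputs are one-sided 0.025, true difference 0, and SD 11 with margin 5.5 or SD 13 with margin 6.5. The normal approximation gives 63 per group. The t-based calculation gives 64, with power 80.1%. The stated 64 per group, and 64 × 3 = 192, reproduce.

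**Standard errors at n = 64 per arm** (df = 126, t = 1.979).
- PHAB: SE = 11 × √(2/64) = 1.945.
- HHIE: SE = 13 × √(2/64) = 2.298.

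**Probability of declaring non-inferiority at n = 64** (noncentral t; the same for both scales in margin units).

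| True test minus AB | Intended rule | Literal rule |
|---|---|---|
| -m (worse by the full margin) | 2.5% | 99.99% |
| -m/2 | 28.9% | 98.8% |
| 0 | 80.1% | 80.1% |
| +m/2 | 98.8% | 28.9% |
| +m | 99.99% | 2.5% |

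The two rules agree at a true difference of 0, which is the planning assumption. The power calculation therefore cannot reveal the slip.

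**Where the two rules disagree.** The intended rule passes when observed d > -(m - t × SE). The literal rule passes when observed d < +(m - t × SE). Inside ±(m - t × SE) both pass; outside it exactly one does.
- PHAB at n = 64: 5.5 - 1.979 × 1.945 = 1.65.
- HHIE at n = 64: 6.5 - 1.979 × 2.298 = 1.95.

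The same formula, with SE = SD × √(1/n₁ + 1/n₂) and the planning SDs, at the group sizes the SAP reports for mild or moderate loss:

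| Comparison (n) | PHAB | HHIE |
|---|---|---|
| Assigned: AB 172, CD 171 | ±3.16 | ±3.74 |
| Assigned: AB 172, EF 180 | ±3.19 | ±3.77 |
| Completers: AB 152, CD 133 | ±2.93 | ±3.46 |
| Completers: AB 152, EF 138 | ±2.95 | ±3.49 |

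**The case against.** The strongest reply is that the bracket is unsigned rather than mis-signed. The SAP prints every margin as a magnitude. Its phrase about distance from zero could take its direction from the context, and the context is plain: the same sentence labels the null, the margin is defined as a boundary of inferiority, and the aim is non-inferiority to AB. The preceding sentence names AB first, and AB minus test would make the positive values correct. The bracket also sits in a power paragraph and is not presented as the analysis rule.

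Most of this stands. It shows that the intended test can be recovered, and it keeps the point minor. It does not remove the contradiction, because the order of subtraction is printed explicitly as test minus AB and the values beside it are positive.

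A second reply is that minus signs were lost when the PDF was read. That is unlikely, since two would have had to vanish while those in the two subtractions survived. It cannot be excluded, because hyphens were lost elsewhere in the SAP text (24item, Biascorrected). Even then, the Analyses paragraph would still lack a confidence-limit criterion.

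A reader might infer that the trial tested the wrong hypothesis, or that its conclusions are reversed. The documents do not support this. Nothing in them shows a reversed test planned or run, and the 99.99% figure applies only if someone applied the bracket literally.

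**Conclusion.** The point holds as a minor but real error in the only numerical statement of the non-inferiority hypothesis. The sign, or the order of subtraction, is wrong for the label attached to it. The size of the margins, alpha, the 64 per arm and the 80.1% power are unaffected.

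The consequence is conditional. Under literal application at 64 per arm, an arm worse by the full margin would pass 99.99% of the time instead of 2.5%. The literal and intended rules would give opposite conclusions for observed differences outside ±1.65 (PHAB) or ±1.95 (HHIE) at n = 64. At the group sizes the SAP reports, the limits are wider: about ±2.9 to 3.2 (PHAB) and ±3.5 to 3.8 (HHIE). All these limits assume the planning SDs of 11 and 13 and an ordinary two-sample t-test on the stated group sizes; the bootstrap and multiple imputation are not modelled.

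**What to change.** 1. In Sample Size and Statistical Power, state H0 as test minus AB ≤ -5.5 for PHAB-global and ≤ -6.5 for HHIE-total benefit. Alternatively, reverse the subtraction to AB minus test and keep the positive margins.
2. In Analyses, state that non-inferiority is concluded when the lower limit of the two-sided 95% confidence interval for test minus AB lies above -5.5 (PHAB) or -6.5 (HHIE). This matches the one-sided 0.025 level and the 95% intervals already planned.
3. Confirm that the analysis code used this direction.

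The cost is one corrected bracket, one added sentence and one check of the code. Sample size, margins and data do not change.

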3.0 Study Protocol

P-CHAT is a three-arm blinded multi-site randomized controlled trial. Individuals (N = 591) between 50 and 79 years old with self-perceived mild or moderate hearing difficulty who have not tried hearing aids previously will be recruited at four clinical study sites. Participants blocked by degree of hearing loss at each site will be randomly assigned in to the Audiology-Based best practice (AB), brief Consumer Decides (CD), and Efficient Fitting (EF) arms. Benefit and satisfaction as well as other outcomes will be measured at 6 weeks and 6 months after hearing aid fitting. The full protocol is included as an appendix.

* The CD group is referred to as the CD group for brevity in the rest of the document.

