11.0 Randomization Method

This section of the MOP describes the randomization approach and procedures, including:

- **Randomization Plan:** The random assignment of sequential enrollees in each hearing-loss severity category to each of the three groups will make use of a site-

specific pre-generated randomized list produced from a random-numbers table. For example, for the targeted total sample of 353 subjects with mild-moderate ARHL, sequential subjects S1, S2, S3, S4, S5, S6, S7, S8...S353 might be assigned, based on a pre-generated randomization, to groups AB, AB, CD, EF, EF, CD, AB, CD...EF.

- **Process Responsibilities:** The randomization table will be generated MPI [name] in consultation with biostatistician [name]. The randomization tables will be stored on REDCap.
- **Procedure for Randomizing a Participant:** The randomization process will be activated as a survey instrument after hearing test results have been supplied during the screening process. The unblinded site audiologist will activate this survey instrument, choose the participant ID, and execute the randomization process by clicking on a button on the survey instrument web page. The audiologist will then change the input to the “Complete?” field on the survey form to mark the process “Complete.” The randomization tables will be maintained during after the study and can be examined at any time.

A video tutorial on the randomization process is available [here](#).

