 - Complete the MoCA test with the participant using a black pen on the paper form
 - Calculate the score and enter the score in REDCap.
 - Upload image of MoCA test form to REDCap.
 - **If MoCA score < 23, participant will be disqualified.**
- Otoscopy
 - Sanitize hands
 - Perform otoscopy on each ear, noting status of ear canals and enter findings in REDCap re: cerumen in each ear:
 - Clear
 - Non-occluding
 - Occluding
- Audiogram
 - Escort participant into test booth and give instructions for pure-tone testing.
 - Use insert earphones
 - Obtain air conduction thresholds in each ear at the following frequencies, using masking as necessary

- Use a black pen to record the responses on the paper [Audiogram](#) form for the following test frequencies:
 - 250
 - 500
 - 1000
 - 2000
 - 3000
 - 4000
 - 6000
 - 8000
- Enter pure tone test results in REDCap.
 - The thresholds for the first ear will be copied and displayed for the second ear. Modify these thresholds to reflect those measured.
- Scan paper audiogram into REDCap. Put paper audiogram into secure file.
- REDCap will calculate PTA for each ear and will display Degree of Hearing Loss based on PTA averaged for both ears.
- **Select the degree of hearing loss displayed by REDCap** (if participant has been pre-assigned to an a study group, the degree will already be selected as “normal” and cannot be changed.

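### Randomisation is stratified on two-ear average PTA, but the SAP's only definition of normal hearing is better-ear PTA4 and its analyses name neither stratification factor

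*SAP*

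**What the plan says.** **Protocol.** Section 3.0: "Participants blocked by degree of hearing loss at each site will be randomly assigned". Section 11.0 describes "The random assignment of sequential enrollees in each hearing-loss severity category to each of the three groups", using site-specific lists. Section 13.4.1 says how the category is obtained: "REDCap will calculate PTA for each ear and will display Degree of Hearing Loss based on PTA averaged for both ears". The audiologist is then told: "Select the degree of hearing loss displayed by REDCap". Section 13.4.5 has site and degree confirmed again when the randomisation button is pressed. Section 13.4.1 adds that a participant already pre-assigned to a study group has the degree preset to normal, and this cannot be altered.

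**SAP.** The sample-size section assumes that about 36% of enrollees will have normal hearing, glossed as "better-ear PTA4 < 20 dB HL". It sets the completion target so that "at least 249 individuals (83 per group) with mild or moderate hearing loss would be included in the analyses". It reports 172, 171 and 180 adults with mild or moderate loss in AB, CD and EF, from 584 enrolled, without restating a PTA rule. The Analyses paragraph says that "sensitivity analyses were performed by examining the outcomes separately for those with mild versus moderate audiometric hearing loss". It lists bootstrapped General Linear Model analyses and t-tests, and gives no model terms.

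Neither document gives the cut-points behind the REDCap categories or the boundary between mild and moderate.

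**The concern.** Two different summaries of the same audiogram are in use. One forms the strata. The other is the only stated rule for who counts as normal and so falls outside the analysis. A participant whose ears differ can be on one side of the line at randomisation and on the other at analysis.

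Three things are at stake:

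- **Membership of the ITT and PP sets.** Both rest on this classification. The SAP is written with enrolment and completion counts known, so an unresolved choice between two rules is an avoidable degree of freedom in a non-inferiority comparison.
- **Balance.** Stratified allocation balances the arms within the categories used. Cutting the population on another variable gives up part of that balance.
- **The model.** If site and degree of loss predict benefit, leaving them out of the analysis gives away precision that the design has already paid for.

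**Working it through.** **1. The plan's own figures.** With margin 5.5, SD 11, one-sided 0.025 and 80% power, the noncentral t calculation gives 64 per group (power 0.801), as stated. HHIE benefit (6.5 and 13) has the same ratio and the same answer. For normal hearing, 249 / (1 - 0.36) = 389.06, stated as 389. For attrition, 389 / (1 - 0.35) = 598.5, or 599, against the stated 591. The stated figure implies 1 - 389/591 = 34.2%, which fits about 35%. None of these figures changes.

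**2. How many are outside the set.** 172 + 171 + 180 = 523, and 584 - 523 = 61, which is 61/584 = 10.4%. I take all 61 to be classed as normal hearing. The SAP does not split them by arm or say which rule classed them.

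**3. An eligible participant on whom the rules disagree.** Thresholds at 0.5, 1, 2 and 4 kHz, with a 15 dB difference at the other frequencies too:

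| Ear | Thresholds (dB) | PTA4 |
|---|---|---|
| Better | 10, 10, 15, 25 | 60/4 = 15 |
| Worse | 25, 25, 30, 40 | 120/4 = 30 |

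This meets every audiometric criterion in Protocol 8.3. Each ear has a threshold above 20 dB, the four-frequency PTA is under 50 dB, and no inter-ear difference exceeds 20 dB. The two-ear average is (15 + 30)/2 = 22.5 dB. With a 20 dB cut on both measures, the average says hearing loss and the better ear says normal.

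**4. Direction.** Better-ear PTA = average - difference/2, so it is never above the average. With the same frequencies and the same cut, people move only from hearing loss to normal. Both conditions are assumptions, because the Protocol states neither REDCap's cut-points nor which frequencies its PTA uses.

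**5. Size (assumed distribution).** I took a normal two-ear average with SD 8-9 dB and an inter-ear difference equal to the absolute value of a normal variable with mean 0 and SD 4-8 dB. I kept pairs with better ear below 50 dB and difference at most 20 dB, as a stand-in for the eligibility rules. The mean was then solved so that exactly 10.4% have better-ear PTA below 20 dB. The share with average at or above 20 dB but better ear below 20 dB is:

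- smallest (SD 9, inter-ear SD 4): 3.1%, and 0.031 x 584 = 18;
- largest (SD 8, inter-ear SD 8): 5.9%, and 0.059 x 584 = 34.

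If the REDCap category formed the set instead, nobody is lost by this route.

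**6. Power.** The smallest completer arm is 133. Two arms of 133 give power 0.98 for a margin of half an SD. After a further 10% cut, to 120, it is 0.97.

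**The case against.** The strongest reply is that the better-ear phrase occurs once, in brackets, explaining a planning assumption taken from earlier trials. The sentence with the actual counts names no rule, and the analysed set may simply be the REDCap category. That stands. The documents show that the rule is unsettled; they do not show that anyone was dropped.

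Three stronger readings are tempting, and the documents support none of them:

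- **The severity subgroups do not match the strata, with some of the moderate stratum becoming mild.** No mild/moderate cut-point or PTA rule is given. The example in Protocol 11.0 even treats mild-moderate as a single group. A mismatch is possible but not shown.
- **The shift must be one-way.** This holds only under the shared-PTA and shared-cut assumptions in step 4.
- **The loss could reach 11%, about 65 people.** That needs a mean average of 28 dB, SD 9 and inter-ear SD 8, which puts about 30% of people below 20 dB by better ear, against 10.4% actually outside the set. If the better-ear rule formed the set, those lost are part of the 61, so 65 is impossible.

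It is also fair to say that the better ear already serves as an eligibility measure (Protocol 13.4.2), so it is not an eccentric choice. It is still not the variable on which allocation was stratified.

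**Conclusion.** The point holds as an inconsistency to resolve. Strata use the two-ear average, the only SAP definition of normal hearing uses the better ear, and the analyses name neither stratification factor. If the better-ear rule forms the set, and both rules use the same PTA and a 20 dB cut, about 3-6% of those enrolled (roughly 18-34 of 584) were randomised in a hearing-loss stratum and then excluded. The range rests on assumed distributions calibrated to the reported 10.4%.

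A reader might infer a biased comparison or an underpowered trial. Neither follows. Hearing level is measured before randomisation, so restricting on it does not bias the arms in expectation, and numbers are ample. The cost is some lost balance and precision, and an analysis set that cannot be identified from the plan.

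**What to change.** - Define the analysis set and the mild and moderate groups by the degree category recorded at randomisation, and state its PTA frequencies and cut-points.
- Include that category and site as factors in the General Linear Model for PHAB global and HHIE-total benefit.
- Handle pre-assigned participants explicitly. Their recorded degree is locked as normal whatever their thresholds, so classify them by measured thresholds for analysis-set membership, say which category they carry in the model, and tabulate them by arm.
- Report the better-ear PTA4 classification as a sensitivity analysis, with a cross-tabulation of the two classifications by arm.

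The cost is a few SAP sentences and a little extra analysis; the thresholds are already in REDCap. The downside is timing. Enrolment and completion counts are known, so the choice of definition must be labelled as made after enrolment, and showing both versions lets the reader judge whether it matters.
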